## 5. STUDY TREATMENT AND CONDUCT

### 5.1 Treatment

MEDI-573 is manufactured by MedImmune. MEDI-573 is supplied as a white to off-white, lyophilized powder in a 10 mL vial. Each vial contains 100 mg (nominal) of active investigational product.

The MEDI-573 formulation is described in [Table 1](#). MEDI-573 must be stored at 2°C to 8°C and must not be frozen.

**Table 1**                      **MEDI-573 Formulation**

Investigational Product	Dosage form and strength	Manufacturer
MEDI-573	Contains 100 mg of MEDI-573	MedImmune

Labels will be prepared in accordance with Good Manufacturing Practice and local regulatory guidelines. Label text will be translated into local language.

Each vial of MEDI-573 will have a label indicating 'For clinical study use'.

Detailed instructions regarding investigational product preparation can be found in 'Procedures for drug storage'.

Date

### **5.1.1 Investigational Product Preparation**

The dose of investigational product for administration must be prepared by the investigational product Manager/site pharmacist using aseptic technique. Detailed instructions regarding investigational product preparation can be found in ‘Procedures for drug storage’ that will be provided to the investigational product Manager/site pharmacist.

MEDI-573 will be reconstituted with 4.0 mL sterile water for injection which gives a final concentration of 25 mg/mL. The reconstituted solution at 25 mg/mL will be further diluted into a saline bag for IV infusion.

To reconstitute the lyophilized product, slowly add 4.0 mL of sterile water for injection to the vial. The vial should be tilted slightly and gently rotated or swirled for 30 seconds or until dissolution is complete. Do not shake or vigorously agitate the vial. This is a critical step to avoid prolonged foaming. Reconstituted MEDI-573 should stand undisturbed at room temperature for a minimum of 2 minutes until the solution clarifies. Reconstituted MEDI-573 does not contain a preservative and should be administered promptly (no longer than 6 hours) after reconstitution. MEDI-573 is used as a single-use vial and any unused portion must be returned to AstraZeneca.

### **5.1.2 Administration of Investigational Product**

All subjects must be weighed (according to institutional practice) prior to a dose on Day 1 of infusion each treatment cycle for calculation of MEDI-573 dosing.

MEDI-573 will be administered to subjects on an outpatient basis as follows:

1. Before the MEDI-573 infusion is started, epinephrine, dexamethasone, and diphenhydramine, or another functionally equivalent H1 blocker, should be prepared for IV administration and resuscitation equipment, because the emergency management of an anaphylactic reaction might be needed.
2. MEDI-573 will be administered once every 7 days as a 60-minute IV infusion in Cohorts 1 and 2 and once every 21 days as a 90-minute IV infusion in Cohort 3. Vital signs (body temperature, respiration rate, pulse, and blood pressure) will be measured according to Section 6.3.3 and will be captured in the subject’s source documents.
3. If a subject experiences an infusion reaction during infusion of MEDI-573, diphenhydramine or the institutional equivalents, may be administered. Alternatively, or in addition, the rate of infusion of MEDI-573 may be diminished. Any such activities must be recorded appropriately. In such subjects who experience an infusion reaction, prophylactic administration of diphenhydramine or the equivalents may be considered for subsequent administration of MEDI-573.
4. In the case of an outpatient, subjects will remain at the study site for at least 60 minutes after the MEDI-573 infusion for medical monitoring.

Date

Since the compatibility of MEDI-573 with other IV medications and solutions, other than 0.9% Sodium Chloride for Injection, is not known, the MEDI-573 solution should not be infused through an IV line in which other solutions or medications are being administered. The date, start time, and completion time of MEDI-573 administration must be recorded in source documents.

### 5.1.3 Starting dose, dose escalation scheme and stopping criteria

The starting MEDI-573 dose is 5.0 mg/kg once per week. The tolerability of this dose was confirmed in the preceding US Phase 1 study (MI-CP 184). The following table presents the dose escalation scheme including dose cohorts and the (maximum) number of evaluable subjects. In addition, the MEDI-573 dose of Cohort 3 will be determined by the result of MI-CP184 study.

**Table 2 Summary of Dose Cohorts**

Dose Cohort	Number of Subjects	MEDI-573 Dose
1	3-6	5.0 mg/kg as a 60-minute IV infusion once every 7 days
2	3-6	15 mg/kg as a 60-minute IV infusion once every 7 days
3	3-6	30 or 45 mg/kg as a 90-minute IV infusion once every 21 days

Subjects will be enrolled to ensure a minimum of 3 and a maximum of 6 evaluable subjects per cohort. Dose escalation will follow the scheme below, according to the following logic:

If no DLT is observed (for definition see Section 5.1.4) in a cohort of 3 evaluable subjects, then dose escalation may occur. Dose increases will be permitted after review of data from a minimum of 3 evaluable subjects has been performed.

If one subject of the 3 evaluable subjects experiences a DLT, then 3 more evaluable subjects will be enrolled to have 6 evaluable subjects. If only one DLT is observed in the complete cohort of 6 evaluable subjects, then dose escalation may occur.

If 2 or more subjects experience a DLT in a group of up to 6 subjects, irrespective of the number of subjects enrolled, the dose will be considered not tolerated and recruitment to the cohort and dose escalation will cease. If the next lower dose level has 3 evaluable subjects, 3 more evaluable subjects will be enrolled to have 6 evaluable subjects.

At the discretion of the sponsor, an intermediate dose may be chosen for dose escalation. Situations that might prompt selection of an intermediate dose include unexpected toxicities that do not meet the definition of DLT or multiple similar toxicities in a cohort that do not meet the definition of a DLT. If an intermediate dose is chosen, subsequent dose escalation will be to the next predetermined dose provided all the criteria for dose escalation in Rules above are met. Further dose escalation will be based on toxicities observed at each dose level,

Date

and may proceed according to the original dosing schedule or may include additional intermediate dosing steps based on accumulated safety data.

There will be no intra-subject dose escalations.

The dose for subsequent cohorts or a decision to stop recruitment will be agreed by the dose escalation committee (DEC) after review of the data from each cohort (see Section **Error! Reference source not found.**).

#### **5.1.4 Definition of dose-limiting toxicity**

DLT will be graded according to the NCI CTCAE V4.0 and will be assessed from Cycle 1, Day 1 through Cycle 1, Day 21.

A DLT is defined as:

1. Any Grade 3 or higher non-haematologic toxicity that occurs during the DLT assessment period where a cause other than the investigational product cannot be reasonably justified with the following exceptions:
  - Grade <4 high glucose (fasting) with a duration of <24 hours after administration of MEDI-573
  - Grade 3 fever (in the absence of neutropenia) defined as >40.0°C (39.5°C in the axilla) that resolves to normal or baseline within 24 hours of treatment and is not considered an SAE
  - Grade 3 rigors/chills that respond to optimal therapy
  - Any isolated or transient laboratory changes without associated clinical signs or symptoms.
2. Any Grade 3 or higher haematologic toxicity that occurs during the DLT assessment period where a cause other than the investigational product cannot be reasonably justified.

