### **3.1 Overall study design and flow chart**

#### **Study Design**

This is a Phase 1, open-label, single-arm, dose-escalation study to evaluate the safety, tolerability, and pharmacokinetics of MEDI-573 in Japanese adult patients with advanced solid tumours refractory to standard therapy or for which no standard therapy exists.

The study will be conducted at one site in Japan.

Subjects are considered evaluable if they receive 3 doses of MEDI-573 (Cohorts 1 and 2) or 1 dose of MEDI-573 (Cohort 3) during cycle 1 and are followed for 21 days from the date of first dose (one cycle) or they discontinue MEDI-573 due to dose-limiting toxicities (DLTs). Each cohort will include 3 to 6 evaluable subjects and a total of 9 to 18 evaluable subjects will be evaluated during the study.

MEDI-573 will be administered once every 7 days (on Days 1, 8, and 15 of each 21-day treatment cycle) as a 60-minute IV infusion in Cohorts 1 and 2 and once every 21 days (Day 1 of each 21-day treatment cycle) as a 90-minute IV infusion in Cohort 3 until unacceptable toxicity, documentation of disease progression, or other reasons for subject withdrawal. Intra-subject dose escalation will not be allowed. On 2nd Cycle and beyond, continuation, interruption or permanent discontinuation of treatment will be decided based on the criteria specified in section 5.1.8. Subjects will be considered to have completed a cycle only when they have received all the specified doses at each cycle, and subjects who do not complete a cycle will discontinue the treatment and not move on to the next cycle. Rules for interruption or discontinuation of MEDI-573 in individual subjects are described in Section 5.4.1. Rules for interruption or discontinuation of MEDI-573 and study entry are described in Section 5.4.2.

Dose escalation will follow a standard 3+3 design. Rules for dose escalation are described in Section 5.1.3.

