#### **5.1.6 Definition of evaluable subject**

Subjects are considered evaluable if they receive MEDI-573 and either:

Date

- have received 3 doses of MEDI-573 (Cohorts 1 or 2) or 1 dose of MEDI-573 (Cohort 3) during the cycle and are followed for 21 days from the date of first dose (one cycle)
- have experienced a DLT during the cycle 1

Subjects who have a delay in drug administration during the DLT evaluation period are considered as unevaluable.

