### **5.1.7 Dose escalation committee**

The DEC will evaluate the safety and tolerability of MEDI-573 collected in the cohort and decide on whether to proceed to dose escalation for the next cohort.

The DEC will consist of:

- Study Team Physician, who will chair the committee, or delegate
- Principal Investigator or representative(s) of the study sites

Sub Investigator from investigational sites, the Study Pharmacokineticist, Study Statistician, Patient Safety Scientist and Study Delivery Team Leader may also be invited as appropriate. The DEC remit document for this study will define the exact membership and who should be present for decisions to be made.

Once there are at least 3 evaluable subjects at a dose level, the DEC will review and assess all available safety data documented by the investigators, if possible, together with available PK data, such as demography, AEs of CTCAE grade  $\geq 2$  observed in the DLT assessment period (Days 1 to 21 in Cycle 1), and whether the beginning of Cycle 2 for MEDI-573 has to be postponed or not, to make a decision on for the next cohort of subjects. Any dose interruptions will be taken into account.

The decision may be to:

1. Proceed with dose escalation – refer to Section [5.1.3](#)
2. Expand the cohort to a maximum of 6 evaluable subjects
3. Stop the dose escalation part of the study

Any subject started on treatment in error, as he/she failed to comply with all of the selection criteria but meets the criteria of an evaluable subject, will be reviewed on a case by case basis by the DEC to determine if the subject should be included or excluded in the decision for dose escalation.

The decisions and decision-making of the DEC on the next dose level will be documented and give a notice to the principal investigators prior to dosing any new subjects.

Date

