**Table 5 Study plan (Cohorts 1 and 2)**

Assessment	Screen	Cycle 1					Cycle 2 and Beyond			End of Treatment d	Follow-up		Details in
		Day 1	Day 2	Day 3	Day 8	Day 15	Day 1	Day 8	Day 15		30 days after the last dose	3 months after the last dose	
Allowance (days)	- 28 - 1	—	—	—	—	—	±2	±2	±2		+3	±14	
Written Informed Consent	X						X a						Appendix D
Verify Eligibility Criteria	X	X											4.1, 4.2
Medical History	X												6.3
Pregnancy test b	X	X					X				X		6.3.5
WHO Performance Status	X	X					X			X	X	X c	6.3.2
Physical Examination	X	X					X			X	X	X c	6.3.2
Height	X												6.3.2
Weight	X	X					X			X	X		5.1.2
Vital Signs	X	X		X	X	X	X	X	X	X	X		6.3.3
ECG	X	X					X			X	X		6.3.4
Haematology/ Clinical Chemistry	X	X		X	X	X	X	X	X	X	X		6.3.5
Urinalysis	X	X			X	X	X	X	X	X	X		6.3.5
Tumour assessment (CT or MRI Scans)	X						X c			X		X c	6.9.1
Tumour marker	X						X c			X		X c	6.9.2
PK f		X	X	X	X	X	X	X g	X g	X	X		6.5
Anti-MEDI-573 Antibodies		X					X				X	X	6.5.3
Blood Biomarker Analysis		X	X	X	X	X	X	X	X	X	X		6.7

Date

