### **6.3.5 Laboratory safety assessment**

Blood and urine samples for determination of haematology, clinical chemistry, and urinalysis will be taken at the visits as indicated in the study schedule (see [Table 5](#) and [Table 9](#)). All assessment timepoints are based on Day 1 as first dose of MEDI-573 and are to be taken with this baseline. Laboratory tests are done on treatment day, it should be done prior to infusion. Laboratory tests do not need to be repeated at baseline if the baseline visit is within 3 days of the screening sample.

The date of each collection will be recorded in the appropriate CRF.

Date

Following review of data from a group of subjects the timing of blood samples may be adjusted for subsequent groups of subject. Laboratory values that meet the criteria for CTCAE grade 3 or have changed significantly from baseline and are considered to be of clinical concern will be repeated/confirmed within 7 days and followed up as appropriate.

The following laboratory variables will be measured:

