## **6.8 Biological sampling procedures**

### **6.8.1 Volume of blood**

The total volume of blood that will be drawn from each subject at screening and during Cycle 1 in this study is shown in [Table 16](#).

Date

**Table 16** Volume of blood to be drawn from each subject during Cycle 1 (including screening period)

		Sample volume (mL)	Number of samples	Total volume (mL)
Safety	Clinical Chemistry	5	5 (4 a )	25 (20 a )
	Haematology	2.6	5 (4 a )	13 (10.4 a )
PK	MEDI-573	4	10 (7 a )	40 (28 a )
IM	Anti-MEDI-573 antibodies	8.5	1	8.5
Exploratory biomarker research	Central laboratory of Sponsor	16	10 (7 a )	160 (112 a )
Soluble protein	Clinical laboratory	5	10 (7 a )	50 (35 a )
Tumour markers b		3.5	1	3.5
TOTAL				300 (217.4a)

a Cohort 3

b Depend on target tumours

The total volume of blood that will be drawn from each subject at cycle 2 in this study is shown in [Table 17](#).

**Table 17** Volume of blood to be drawn from each subject during Cycle 2

		Sample volume (mL)	Number of samples	Total volume (mL)
Safety	Clinical Chemistry	5	3 (2 a )	15 (10 a )
	Haematology	2.6	3 (2 a )	7.8 (5.2 a )
PK	MEDI-573	4	6 (2 a )	24 (8 a )
IM	Anti-MEDI-573 antibodies	8.5	1	8.5
Exploratory biomarker research	Central laboratory of Sponsor	16	6 (2 a )	96 (32 a )
Soluble protein	Clinical laboratory	5	6 (2 a )	30 (10 a )
TOTAL				181.3 (73.7a)

a Cohort 3

b Depend on target tumours

The total volume of blood that will be drawn from each subject at Cycle 3 and beyond in this study is shown in [Table 18](#).

Date

**Table 18** Volume of blood to be drawn from each subject during Cycle 3 and beyond

		Sample volume (mL)	Number of samples	Total volume (mL)
Safety	Clinical Chemistry	5	3 (2 a )	15 (10 a )
	Haematology	2.6	3 (2 a )	7.8 (5.2 a )
PK	MEDI-573	4	2	8
IM	Anti-MEDI-573 antibodies	8.5	1	8.5
Exploratory biomarker research	Central laboratory of Sponsor	16	2	32
Soluble protein	Clinical laboratory	5	2	10
Tumour markers b		3.5	1	3.5
TOTAL				84.8 (77.2a)

a Cohort 3

b Depend on target tumours and only on Day 1 of odd cycles (pre-dose)

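### In the weekly cohorts no safety laboratory test is scheduled between the third infusion and the end of the DLT window, so a cytopenia first seen at Cycle 2 Day 1 has no clear place in the 3+3 count

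*Protocol*

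**What the plan says.** Section 5.1.4 fixes the window: "DLT will be graded according to the NCI CTCAE V4.0 and will be assessed from Cycle 1, Day 1 through Cycle 1, Day 21". Any Grade 3 or higher haematologic toxicity in that window is a DLT unless another cause can reasonably be justified. The exception for isolated or transient laboratory changes without symptoms is listed under the non-haematologic item only.

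Section 5.1.7 gives the dose escalation committee (DEC) adverse events of Grade 2 or higher "observed in the DLT assessment period (Days 1 to 21 in Cycle 1", within its review of all available safety data.

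Section 5.1.6 makes a subject in Cohorts 1 and 2 evaluable after three doses and 21 days of follow-up from the first dose, or after a DLT. Table 20 defines the MTD set in similar terms: a full cycle and safety follow-up through the DLT period, or a DLT.

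Section 3.1 sets the weekly infusions at Days 1, 8 and 15. Table 5 schedules haematology and chemistry at screening, on Cycle 1 Days 1, 3, 8 and 15, and then on Cycle 2 Day 1. Section 6.3.5 adds: "Laboratory tests are done on treatment day, it should be done prior to infusion".

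**The concern.** The plan makes the third infusion a condition of evaluability but schedules no blood count inside the DLT window that could show its effect. A cytopenia usually needs a blood count to be seen, and it belongs to the DLT category with no listed laboratory exception. If one caused by the third infusion first shows in the Cycle 2 Day 1 sample, whether it counts depends on the visit day or on a judgement of when it began.

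The reporting rule adds to this. Under Section 6.4.3, deterioration in a laboratory value is itself reported as an adverse event only if it is an SAE, a DLT or the reason for stopping treatment. An asymptomatic Day 22 cytopenia ruled not to be a DLT because of its timing may therefore not be recorded as an adverse event at all.

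The 3+3 count in Section 5.1.3 governs escalation from each cohort, and Section 5.1.5 derives any MTD from it. A missed DLT moves the decision towards calling the dose tolerated. Cytopenia is plausible on the Protocol's own evidence: Section 2.2.2 reports anaemia and thrombocytopenia, assessed as possibly related, in one subject who stopped treatment in MI-CP184, and Section 5.3 cites Grade 3/4 thrombocytopenia with similar antibodies.

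**Working it through.** **Step 1. Reproduce the planned number of samples.** From the row "Haematology/ Clinical Chemistry" in Table 5: screening + Days 1, 3, 8, 15 = 1 + 4 = 5. Table 16 states 5 chemistry and 5 haematology samples for screening plus Cycle 1. The volumes agree: 5 × 5 mL = 25 mL and 5 × 2.6 mL = 13 mL. So does the total: 25 + 13 + 40 + 8.5 + 160 + 50 + 3.5 = 300 mL. No further safety sample is hidden elsewhere in the cycle.

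**Step 2. Assign each sample to the infusion it follows,** using the pre-infusion rule of Section 6.3.5.

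| Infusion | Scheduled safety samples before the next infusion or Day 21 |
|---|---|
| Day 1 | Day 3, Day 8 (pre-dose) |
| Day 8 | Day 15 (pre-dose) |
| Day 15 | none |

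The next sample is Cycle 2 Day 1: 21 + 1 = Day 22. The ±2-day allowance in Table 5 alone gives Days 20 to 24. The 6-day minimum dosing interval in Section 5.1.8 makes the earliest day 15 + 6 = Day 21. A sample inside the window is thus permitted but not required.

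In Cohort 3 the only Cycle 1 infusion is followed by samples on Days 3 and 8, so this point is confined to the weekly cohorts.

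**Step 3. Illustrate the effect on the 3+3 decision.** A cohort is called tolerated with 0 of 3 DLTs, or with 1 of 3 and then 0 of 3. With DLT probability p and q = 1 − p:

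P(tolerated) = q³ + 3pq² × q³ = q³ + 3pq⁵

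The Protocol gives no DLT rates, so these are assumptions:
- A: all DLTs are laboratory-detected, one third first appear after the third infusion, and none of that third is counted. The counted rate is p × (1 − 1/3) = 2p/3.
- B: as A, but only half of DLTs are laboratory-detected. The counted rate is p × (1 − 1/6) = 5p/6.

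| True p | P(tolerated), all counted | A: counted rate | A: P(tolerated) | B: counted rate | B: P(tolerated) |
|---|---|---|---|---|---|
| 10% | 0.906 | 6.7% | 0.955 | 8.3% | 0.932 |
| 30% | 0.494 | 20% | 0.709 | 25% | 0.600 |
| 40% | 0.309 | 26.7% | 0.564 | 33.3% | 0.428 |

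Example for 30% under A: 0.7³ + 3 × 0.3 × 0.7⁵ = 0.343 + 0.151 = 0.494, against 0.8³ + 3 × 0.2 × 0.8⁵ = 0.512 + 0.197 = 0.709.

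**Step 4. Check with a different assumption.** Suppose an equal, independent laboratory-DLT risk h per infusion, visible for two of three infusions.
- h = 5%: cycle risk 1 − 0.95³ = 14.3%, visible 1 − 0.95² = 9.8%; P(tolerated) goes from 0.828 to 0.910.
- h = 10%: 27.1% and 19.0%; from 0.555 to 0.730.

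The direction is the same, and the size again depends on the assumed rate.

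**The case against.** Much of the case on the other side stands, and it narrows the point.

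- **Occurrence against detection.** A reader might infer that any Day 22 finding is excluded. The text does not go so far: Section 5.1.4 counts toxicity that occurs in the window, and a low count on Day 22 may have arisen by Day 21. The 21-day follow-up in Section 5.1.6 can also be read as reaching nominal Day 22. This makes the status unclear, which is the point to be settled.
- **Other routes to the decision.** The DEC reviews all available safety data and whether the start of Cycle 2 had to be postponed. Section 5.1.3 allows an intermediate dose for toxicities short of a DLT, and Section 6.3.5 allows unscheduled follow-up of abnormal values and later changes in sample timing. These are real safeguards, but discretionary ones, and they do not settle whether the finding enters the formal count.
- **Chemistry.** A reader might extend the point to all laboratory toxicity. Isolated or transient non-haematologic changes without symptoms are exempt, and symptomatic DLTs still count through Day 21, so the gap is mainly haematologic.
- **Exposure.** A reader might infer that accumulation makes the third infusion the one with the highest exposure. The Protocol gives no human half-life or accumulation figure; Section 7.4 leaves the accumulation ratio to be estimated. The point does not need this.
- **Rates.** Section 2.2.2 reports no DLT in 25 subjects, 10 of them at 15 mg/kg. If all were DLT-evaluable (an assumption), the one-sided 95% upper bounds are 1 − 0.05^(1/25) = 11% and 1 − 0.05^(1/10) = 26%. Rates of 30% to 40% are therefore pessimistic for the doses studied, although those subjects were not in the Japanese trial population.
- **Cohort 3.** Section 5.1.3 takes its dose from MI-CP184, so its dose level does not rest on this count. Whether to proceed to it still depends on the 3+3 rule.

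**Conclusion.** The gap is real and narrow. In Cohorts 1 and 2, scheduled safety laboratory tests inside the DLT window follow two of the three Cycle 1 infusions. The Protocol does not say how to count a haematologic toxicity of the third infusion that is first seen at Cycle 2 Day 1.

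The effect is small if true DLT rates are low: 91% to 95% at a true 10% rate under assumption A, and 91% to 93% under B. It is substantial if they are high: at 30%, 49% to 71% under A and 49% to 60% under B. All these figures rest on assumed rates and detection patterns. They show direction and range; the largest should not be read as the expected error. The Protocol does not support saying that such toxicity is certain to be excluded or that escalation decisions would be unsound. The correction is nonetheless cheap and removes an ambiguity from the count behind the primary decision.

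**What to change.** Reconcile three things: the DLT window (Sections 5.1.4 and 5.1.7), the evaluability follow-up (Section 5.1.6 and Table 20) and the laboratory schedule (Table 5 and Section 6.3.5). One way is to state that findings in the already scheduled Cycle 2 Day 1 pre-dose laboratory sample count as Cycle 1 DLT data.

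Two details need wording so that the window has a defined end:
- Subjects who do not continue (Cycle 2 needs separate consent under Section 5.1.9) should have their end-of-treatment laboratory sample within the same Cycle 2 Day 1 visit window, because Table 5 gives that visit no fixed day.
- The text should say which sample closes the window if the Cycle 2 infusion is postponed.

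The cost is amendment wording. Continuing subjects need no new visit or blood draw; subjects who stop need a defined day for a sample already planned. The DEC decision may come a few days later: with samples on Days 21 to 24, up to 24 − 21 = 3 days after the present end of the window.

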#### **5.4.2 Interruption or Discontinuation of Study Dosing and Entry**

If any of the following occur, no further administration of investigational product will take place and no further subjects will be entered into the study:

1. Death in any subject in which the cause of death is related to investigational product
2. Anaphylactic reaction to investigational product in any subject; or
3. Other events that in the judgment of the study team physician are serious enough to warrant immediate review by the DEC

If one of the above-listed events occurs, a prompt review of safety data and the circumstances of the event in question will be conducted by the study team physician and the DEC to determine whether dosing and study entry should be resumed, whether the protocol will be modified, or whether the study will be discontinued permanently. Review and approval by the DEC are required for resumption of the study in the event the study is interrupted because of one of the above-listed events.

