### **Adverse events based on examinations and tests**

The results from protocol mandated laboratory tests, vital signs, ECGs and other safety assessments will be summarised in the Clinical Study Report. Deterioration as compared to baseline in these parameters will therefore only be reported as AEs if they fulfil any of the criteria for a SAE or DLT, or are the reason for discontinuation of treatment with the investigational product unless clearly due to progression of disease under study (see Disease progression).

If deterioration in a laboratory value, vital sign, ECG or other safety assessment is associated with clinical signs and symptoms, the sign or symptom will be reported as an AE and the associated laboratory result or other finding will be considered as additional information.

Date

Wherever possible the reporting investigator uses the clinical, rather than the laboratory term (eg, anaemia versus low haemoglobin value).

Deterioration of a laboratory value that is unequivocally due to disease progression should not be reported as an AE.

Any new or aggravated clinically relevant abnormal medical finding at a physical examination as compared with the baseline assessment will be reported as an AE.

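### Section 5.1.4: the laboratory exception to the DLT definition does not exclude glucose, so it can exempt symptom-free hyperglycaemia that the glucose exception leaves as a DLT

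*Protocol*

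**What the plan says.** Protocol Section 5.1.4 makes a Grade 3 or higher non-haematologic toxicity in Cycle 1, Days 1 to 21, a DLT if no cause other than the product can reasonably be justified. Four exceptions follow as a list.

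- The first is "Grade <4 high glucose (fasting) with a duration of <24 hours after administration of MEDI-573".
- The second and third concern fever and rigors. The fever exception carries grade, time and seriousness limits.
- The fourth is "Any isolated or transient laboratory changes without associated clinical signs or symptoms".

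The haematologic criterion that follows has no exceptions.

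Section 5.1.3 turns the DLT count into action. No DLT in three evaluable subjects permits escalation. One in three requires three more subjects, after which "If only one DLT is observed in the complete cohort of 6 evaluable subjects, then dose escalation may occur". Two or more in up to six mean that the dose is not tolerated and that recruitment and escalation stop. Section 5.1.5 places the MTD one level below a non-tolerated dose.

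Under Section 6.4.3, a worsened laboratory value will "only be reported as AEs if they fulfil any of the criteria for a SAE or DLT", or if it leads to discontinuation of treatment.

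**The concern.** The exceptions are alternatives: meeting any one is enough. The sponsor evidently meant Grade 4 glucose, and Grade 3 glucose lasting a day or more, to stay DLTs, because the first exception stops short of both. The fourth then exempts laboratory changes in general. It defines neither *isolated* nor *transient*, and because the two are joined by *or*, an isolated change need not be brief. No rule says that the specific glucose exception prevails over the general one.

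Two careful readers could therefore classify the same glucose value differently, and three things turn on the answer.

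- **The 3+3 action.** One such subject can move a cohort from escalate to expand or, if there is another DLT, to stop.
- **Evaluability.** In Cohorts 1 and 2 a subject who stops before the third dose is evaluable only if the event was a DLT (Section 5.1.6). Otherwise the subject is replaced (Section 5.4.1) and leaves the count.
- **What the DEC is shown.** An exempted value need not be recorded as an AE, so it can fall outside the Grade 2 or higher AEs that Section 5.1.7 names.

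Glucose is a relevant signal: Section 5.3 cites Grade 3 hyperglycaemia for similar antibodies.

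**Working it through.** The protocol states no figure to reproduce here. The check has two parts.

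**1. Logic of the exceptions.** Take symptom-free fasting high glucose and cross grade (3 or 4), duration (under 24 hours, or 24 hours or more), isolated (yes or no) and transient (yes or no): 2 × 2 × 2 × 2 = 16 cases.

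- The first exception covers Grade 3 under 24 hours: 4 cases. The other 12 fail it.
- The fourth exception covers every case that is isolated, transient or both: 9 of those 12.
- The remaining 3, neither isolated nor transient, stay DLTs.

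These are counts of cases, not probabilities. They show that the first exception's limits are bypassed for part of the symptom-free events, not all.

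**2. Effect on the 3+3 rule.** Inputs:

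- *u*, the rate of undisputed DLTs: 0 to 0.11. Section 2.2.2 reports no DLT among 25 US subjects. The one-sided 95% upper limit is 1 − 0.05^(1/25) = 0.113, rounded to 0.11. It is a loose guide, because that study's DLT definition is not shown.
- *d*, the rate of disputed glucose events: 1% and 2%. These are assumptions.
- The two are treated as separate events, so the DLT rate is *p* = *u* if disputed events are exempt and *p* = *u* + *d* if they count.

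With q = 1 − p, a cohort passes with probability

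Pass(p) = q³ + 3pq⁵.

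A cohort that passes with disputed events counted also passes with them exempt. The difference in Pass is therefore the chance that the final results differ.

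The action after three subjects differs when at least one subject is disputed and at most one has an undisputed DLT:

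1 − (1 − d)³ − 3u²d.

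| u | d | Pass, exempt | Pass, counted | Final result differs | Action after three differs |
|---|---|---|---|---|---|
| 0 | 1% | 1.0000 | 0.9988 | 0.0012 | 0.0297 |
| 0 | 2% | 1.0000 | 0.9954 | 0.0046 | 0.0588 |
| 0.11 | 1% | 0.8892 | 0.8715 | 0.0178 | 0.0293 |
| 0.11 | 2% | 0.8892 | 0.8529 | 0.0364 | 0.0581 |

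Now suppose exactly one disputed event has occurred among the first three subjects, with none later, and let q = 1 − u.

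- The immediate action differs unless both other subjects have a DLT: 1 − u², which is 1.000 at u = 0 and 0.988 at u = 0.11.
- The final result differs with probability q²(1 − q³) + 2uq·q³. This is 0 at u = 0. At u = 0.11 it is 0.7921 × 0.2950 + 0.1958 × 0.7050 = 0.372.

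**Can the 24-hour limit be checked?** Tables 13 to 16 appear to schedule glucose at 2, 6, 24 and 48 hours after the Day 1 dose, although they do not specify fasting. After the Day 8 and Day 15 doses in Cohorts 1 and 2, Table 13 plans only pre-dose and end-of-infusion samples.

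**The case against.** The best defence is that a specific provision governs over a general one. Glucose is the only analyte with its own exception, so the fourth can be read as covering other laboratory values. That is natural and probably intended, but no sentence says it, and a DLT rule should not depend on a convention of interpretation.

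The second defence is discretion. Escalation is permissive. The sponsor may choose an intermediate dose for "unexpected toxicities that do not meet the definition of DLT or multiple similar toxicities". The DEC reviews all available safety data, with the Grade 2 or higher AEs given only as examples, and may expand or stop. Section 5.4.2 allows a halt for "Other events that in the judgment of the study team physician are serious enough to warrant immediate review by the DEC". A serious glucose value could also be reported as an SAE. All of this stands and makes an unnoticed Grade 4 glucose unlikely at a single site. None of it settles whether the value counts in a rule whose expansion and stopping steps are mandatory.

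The third is rarity. Section 4.2 excludes poorly controlled diabetes, hyperglycaemia is not among the common US AEs in Section 2.2.2, and Section 5.3 says the antibody may spare glucose homeostasis. This stands, and it limits the size of the point.

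A reader might also infer that the glucose limits do nothing for any symptom-free event. The text does not support that: a change that is neither isolated nor transient remains a DLT.

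**Conclusion.** The wording problem is real and narrow. Read literally, the fourth exception exempts symptom-free fasting hyperglycaemia that is isolated or transient, even where the first exception deliberately leaves it as a DLT. It is an overlap that defeats the evident purpose of the glucose limits, not a formal contradiction.

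The expected effect is small: under the assumed rates, a different final pass or stop in about 0.1% to 3.6% of cohorts, with the upper end needing an 11% undisputed DLT rate. The near-certain change in the immediate action applies only once a disputed event has occurred and does not mean that such events are likely.

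It might also be inferred that every symptom-free Grade 4 chemistry value ought to be a DLT. Whether to exempt values other than glucose is a design choice for the sponsor, and the protocol sets no limit of its own that such an exemption would defeat. The point rests on glucose, where it does. It merits correction because the rule drives dose decisions and the change is very small.

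**What to change.** In Section 5.1.4, add to the fourth exception: other than high glucose, which is governed only by the first exception. In Section 5.1.7, have all Cycle 1 Grade 3 or higher laboratory values listed for the DEC, whether or not they are called DLTs.

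Optionally, the sponsor may limit the fourth exception to Grade 3 for other chemistry values and require recovery within a stated time. Section 6.3.5 offers an anchor, since Grade 3 values of clinical concern "will be repeated/confirmed within 7 days and followed up as appropriate".

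The cost is one clause and one listing. Slightly more events may count as DLTs, so a cohort may be expanded or stopped a little more often. A Grade 3 glucose after a Day 8 or Day 15 dose may need an unscheduled repeat to establish whether it lasted 24 hours. The 7-day repeat is too late for that, but the existing first exception already implies the need.
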